1.2. Study Design

Study V25L-002 is a multicenter, evaluator-blind, randomized, parallel-group, controlled study of the safety and effectiveness of JUVÉDERM VOLUX™ XC injectable gel for jawline restoration. Jawline restoration of each side of the jawline (left and right) will be assessed independently by an EI from cropped 2D [REDACTED] profile images using the ALJDS, an assessment of loss of jawline definition measured by a 5-point scale (0=None to 4=Extreme). Participants randomized to JUVÉDERM VOLUX™ XC will receive injectable gel (initial treatment) to restore jawline definition, provide a smooth contour, and achieve an aesthetically pleasing result. A touch-up treatment, if needed, will be given 30 days after initial treatment with an optional maintenance treatment available 12 months after the last treatment (initial or touch-up) received. At the initial and touch-up (if performed) treatments, the TI will determine the appropriate volume to inject to achieve at least a 1-grade improvement on the ALJDS based on clinical experience, but the maximum volume will not exceed 8.0 mL for initial and touch-up treatments combined. Injection volume for the maintenance treatment will not exceed 8.0 mL.

The following treatment groups are defined for this study:

- ! VOLUX: JUVÉDERM VOLUX™ XC injectable gel
- ! Control: No-treatment Control

Up to 20 investigational sites will enroll up to 280 participants and follow participants who meet the study criteria. Each site will have a blinded EI and a principal investigator who is responsible for the overall conduct of the study at that site and may also be the TI. The TI performs all study treatments, and the blinded EI evaluates ALJDS, GAIS, and facial sensation measurements.

The study design is presented in [Figure 1-1](#). The study will span a total of approximately 26 months: an estimated 6 months for recruitment and 20 months for follow-up. Up to

CONFIDENTIAL

JUVÉDERM VOLUX™ XC

[figure not shown]
Statistical Analysis Plan V25L-002

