The primary effectiveness variable is restoration of jawline definition based on the ALJDS evaluated by EIs. The primary effectiveness endpoint is the proportion of ALJDS responders at Month 6. A responder is defined as a participant who shows at least a 1-point improvement from baseline (pretreatment) on the ALJDS on both sides of the jaw.

Month 6 refers to 6 months after the last treatment (initial or touch-up) for participants in the treatment group and 6 months after randomization for participants in the control group.

The study device will be determined to be clinically effective if at least 50% of participants in the treatment group are observed to be responders on ALJDS at Month 6 and if the responder rate for the treatment group is statistically superior to the responder rater for the control group at Month 6. The following hypotheses will be tested:

$$H_0: P_v < 50\%$$

$$H_a: P_v \geq 50\%$$

and

$$H_0: P_v \leq P_c$$

$$H_a: P_v > P_c$$

where P_v and P_c denote the responder rates for the treatment group at Month 6 after the last treatment (initial or touch-up) and for the control group at Month 6 after randomization, respectively.

The primary effectiveness analysis will be performed based the mITT population using multiple imputation as described in Section 5.3.2. Missing values will be imputed using multiple imputation method. The pooled responder rates and 2-sided 95% CI for the responder rates in the treatment group and in the control group respectively, the pooled between-group difference in the responder rate and the corresponding 2-sided p-value will be calculated, by pooling the results from the 30 imputed data sets using PROC MIANALYZE with normal approximation in SAS.

The first hypothesis will be tested using the pooled 2-sided 95% CI for the responder rate in the treatment group. The null hypothesis will be rejected if the lower bound of the 95% CI is greater than or equal to 50%.

The second hypothesis will be tested using the pooled between-group difference in the responder rate and the corresponding p-value for the between-group difference. The null hypothesis will be

CONFIDENTIAL

Statistical Analysis Plan V25L-002

JUVÉDERM VOLUX™ XC

rejected if the 2-sided p-value is < 0.05 and the responder rate is greater for the treatment group than the control group.

In addition, the 95% CI on the proportion of responders based on the pooled estimate from the 30 imputed data sets will be provided for each treatment group.

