5.1. General Considerations

- ! The primary analysis will be performed after the database is locked and randomization schedule is released.
- ! The Control Period (CP), Treated Period (TP) and Maintenance Treatment Period (MP) are defined in [Table 5-1](#). Note, for participants randomized to the treatment group TP is period between initial treatment and maintenance treatment, which includes CP plus the follow-up period. For participants randomized to the control group TP is the follow-up period once the participants receive optional treatment. Follow-up Period (FP) starts on the end date of CP and ends on the same day as TP.

Table 5-1 Definition of the Control, Treatment and Maintenance Treatment Periods by Randomization Group

Randomization Group	Period	Treatment Group Label	Start Date	End Date
Treatment	CP	VOLUX	Initial treatment date	
The end date is the date of the Month 6 assessment:
 
 ! If multiple assessments fall into the Month 6 window, the date of the assessment included in the Month 6 analysis will be used as end date. ! For participants who exit before Month 6, the end date is study exit date. ! For participants with a missing assessment at Month 6, the end date is the target day for Month 6 (181 days from preceding treatment).
	TP	VOLUX	Initial treatment date	Date of maintenance treatment or the study exit date, whichever is earlier
	MP	VOLUX	Maintenance treatment date	Study exit date
Control	CP	Control	Randomization date	
For participants who do not receive optional treatment:
 
 ! If multiple assessments fall into the Month 6 window, the date of the assessment included in the Month 6 analysis will be used as end date. ! For participants who exit before Month 6, the end date is study exit date. ! For participants with missing assessment at Month 6, the target day for Month 6 (181 days from randomization date) will be the end date. ! For participants who receive optional treatment: the end date is the date of when the optional treatment is received.
	TP	VOLUX-Treated Control	Optional initial treatment date	Study exit date

- ! For CP, effectiveness analyses and baseline characteristics will be performed on the mITT population using the “as-randomized” assignment.
- ! For TP, effectiveness and safety summaries will be performed on the VT population using as-treated grouping.

- ! For MP, effectiveness and safety summaries will be performed on the VMT population.

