5.6.3. Adverse Events

An AE will be considered a TEAE if the AE began or worsened (increased in severity or became serious) on or after the date (and time, if known) of the initial treatment for the treatment group and on or after the date of randomization for the control group. An AE will be considered a TESAE if it is a TEAE that additionally meets any SAE criterion.

A TEAE will be considered a treatment-related AE if the TEAE is deemed related to the procedure or the study device by the TI.

CONFIDENTIAL

JUVÉDERM VOLUX™ XC

Statistical Analysis Plan V25L-002

An AESI is defined as any vision-related TEAE. The incidence of AESI will be summarized separately for CP, TP, and RP in descending order of PT, if the total number of participants with AESI is at least 5.

Overall summary will be provided on a per-participant level for TEAEs, treatment-related TEAEs, TESAEs, deaths, and TEAEs leading to study intervention discontinuation. If more than one event is coded to the same PT for the same participant, the participant will be counted only once for that PT using the greatest severity for the summarizations by severity and most related occurrence for the summarizations by relationship to study intervention. If the severity of a TEAE is missing, the maximum severity will be assigned to the event for the summarization by severity. The value will be displayed as missing in the data listing. If the relationship to the study intervention is missing for a TEAE, the event will be considered related to the study intervention for the summarization. The value will be displayed as missing in the data listing.

TEAEs will be summarized by treatment group for CP using the Safety population. TEAEs will also be summarized for TP and RP using the VT and VRT populations, respectively.

The number and percentage of participants with TEAEs and the events in the following AE categories will be summarized for the above populations as described in [Table 5-10](#). For participants who received maintenance treatment, their AEs reported during the three months in the initial treatment period will be summarized and presented in parallel with AEs reported during the maintenance treatment period.

Summary tables will be provided for participants with TESAEs and participants with TEAEs leading to discontinuation if these occurred in 5 or more participants. Listings of all TEAEs, AESIs, TESAEs, TEAEs leading to discontinuation, and death will be presented.

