Table 6-3 Effectiveness Analysis Visit Definitions for Treatment Group during the Treated Period

Scheduled Visit for Effectiveness Measure	Target Day of the Visit	Analysis Visit Window
Screening ^a	N/A	Screening visit; No more than 30 days prior to randomization
Baseline	N/A	Randomization/Initial Treatment visit
Touch-up Treatment ^b	Day 31 Post Initial Treatment	Day of the Touch-up Treatment
Last Treatment ^c	Day 1 Post Last Treatment	Day 1
Month 1	Day 31 Post Last Treatment	Day 2 to Day 61
Month 3	Day 91 Post Last Treatment	Day 62 to Day 136
Month 6	Day 181 Post Last Treatment	Day 137 to Day 226
Month 9	Day 271 Post Last Treatment	Day 227 to Day 316
Month 12	Day 361 Post Last Treatment	Day 317 to Day of Maintenance Treatment ^d or Day of Study Exit, whichever is earlier

^a Participants may have screening and randomization on the same day. In such cases, only randomization visit is relevant.

^b Not all participants will receive touch-up treatment.

^c If touch-up is not performed then reference date is the date of initial treatment, otherwise reference date is the date of touch-up treatment.

^d Not all participants will receive maintenance treatment.

Table 6-4 Effectiveness Analysis Visit Definitions for Control Group during the Control Period

Scheduled Visit for Effectiveness Measure	Target Day of the Visit	Analysis Visit Window with Touch-up
Randomization Day ^a	Day 1	N/A
Month 1	Day 31	Day 2 to Day 61
Month 3	Day 91	Day 62 to Day 136
Month 6	Day 181	Day 137 to Day of Optional Treatment or Day of Study Exit, whichever is earlier

^a Participants may have screening and randomization on the same day. In such cases, only randomization visit is relevant. Randomization date is the reference date.

Table 6-5 Effectiveness Analysis Visit Definitions for Control Group during the Treated Period

Scheduled Visit for Effectiveness Measure	Target Day of the Visit	Analysis Visit Window
Optional Treatment	N/A	Initial Treatment visit
Touch-up Treatment ^a	Day 31 Post Initial Treatment	Day of the Touch-up Treatment
Last Treatment ^b	Day 1 Post Last Treatment	Day 1
Month 1	Day 31 Post Last Treatment	Day 2 to Day 61
Month 3	Day 91 Post Last Treatment	Day 62 to Day 136
Month 6	Day 181 Post Last Treatment	≥ Day 137

^a Not all participants will receive touch-up treatment.

^b If touch-up is not performed then reference date is the date of initial treatment, otherwise reference date is the date of touch-up treatment.

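### The control-period adverse-event tables count over periods whose length differs by arm and touch-up status, so crude all-cause TEAE percentages are partly confounded with follow-up time

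*SAP*

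**What the plan says.** SAP 5.6.3 sets the between-group safety display: "TEAEs will be summarized by treatment group for CP using the Safety population". Counting starts "on or after the date (and time, if known) of the initial treatment for the treatment group and on or after the date of randomization"; the last clause applies to controls. Protocol 6.2.3.1 has the VOLUX group treated on the day of randomization, so the two starting points coincide.

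The end points do not. In SAP Table 5-1 (Section 5.1) the VOLUX CP ends at the Month 6 assessment. SAP Section 2 fixes the anchor: "Month 6 refers to 6 months after the last treatment (initial or touch-up) for participants in the treatment group and 6 months after randomization"; here too the last clause applies to controls. SAP Table 6-3 gives the VOLUX target as "Day 181 Post Last Treatment". SAP 1.2 adds: "A touch-up treatment, if needed, will be given 30 days after initial treatment". For a VOLUX participant still in the study whose Month 6 assessment is missing, Table 5-1 again counts from the preceding treatment.

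For controls, Table 5-1 uses Month 6 after randomization, with one exception: "For participants who receive optional treatment: the end date is the date of when the optional treatment is received". Protocol Table 5 lets that treatment fall on the day of the Month 6 visit or up to 14 days later.

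Table 5-9 specifies only categorical and event descriptive statistics. Section 5.6.1 measures exposure as injected volume. Neither document specifies follow-up time by arm, a person-time rate or a common cut-off for these tables.

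**The concern.** Timing Month 6 from the last treatment is a deliberate choice for effectiveness: it measures durability at a fixed interval after treatment is complete. Used for AE counting, the same anchor makes the time at risk depend on arm and on whether a touch-up was given. An event unrelated to the device, such as a cold or a headache, has about a month longer to be counted in a VOLUX participant with a touch-up. It has up to two weeks longer in a control who takes late optional treatment.

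This matters because the CP tables are the only AE tables with a concurrent untreated arm. The treated-period and maintenance-period tables cover VOLUX-treated participants only. Elsewhere Section 5.6.3 does match time: it sets AEs from three months of the initial treatment period beside those of the maintenance period. The CP tables have no such matching.

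**Working it through.** **The plan's own figures.** The documents state no CP length for the AE tables, so it has to be built from the target days. The one numerical safety claim (SAP Section 3: at least 92% power with 176 treated and 1.5% incidence) reproduces as the chance of seeing at least one event, 1 - 0.985^176 = 0.930. The present point does not depend on it.

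**Inputs**
- Month 6 target: Day 181 after last treatment (VOLUX) or after randomization (control); SAP Tables 6-3 and 6-4.
- Touch-up: 30 days after initial treatment, window -2/+10 days, so 28 to 40 days; SAP 1.2, Protocol Table 2.
- Optional treatment of controls: 0 to 14 days after Month 6; Protocol Table 5.
- Touch-up share f: not given; assumed 40-80%.
- Background all-cause TEAE risk over 181 days, p: not given; assumed 20-40%, with the same constant hazard in both arms.

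**Step 1: nominal CP length**

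| Participant | CP length (days) |
|---|---|
| VOLUX, no touch-up | 181 |
| VOLUX, touch-up | 30 + 181 = 211 (209 to 221 over the touch-up window) |
| Control, no optional treatment, or treated on the Month 6 visit day | 181 |
| Control, optional treatment 14 days later | 181 + 14 = 195 |

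A touch-up participant has 30 days more than a 181-day control (211/181 = 1.166, or 16.6% more) and 16 days more than a 195-day control (211/195 = 1.082, or 8.2% more). A VOLUX participant without a touch-up has up to 14 days less than a control. These figures hold Month 6 at its target day; its ±10-day visit window widens all of them.

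**Step 2: risk from time alone.** Risk over T days = 1 - (1 - p)^(T/181).

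| p (181 days) | 195 days | 211 days | Excess, 211 vs 181 |
|---|---|---|---|
| 20% | 21.4% | 22.9% | 2.9 points |
| 30% | 31.9% | 34.0% | 4.0 points |
| 40% | 42.3% | 44.9% | 4.9 points |

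**Step 3: arm level.** VOLUX risk = p + f × excess. Subtract the control risk at 181 or 195 days. There is no device effect in this calculation.

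| p | f | All controls 181 days | All controls 195 days |
|---|---|---|---|
| 20% | 40% | +1.2 | -0.2 |
| 20% | 80% | +2.3 | +1.0 |
| 40% | 40% | +1.9 | -0.4 |
| 40% | 80% | +3.9 | +1.6 |

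Mean VOLUX CP is 181 + 30f days. It equals 195 days at f = 14/30 = 47%, which is where the sign turns if every control is treated at 14 days. With no touch-ups and all controls at 195 days, the difference is -1.4 points (p = 20%) to -2.3 points (p = 40%).

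**Step 4: does a rate remove it?** For p = 20%, the hazard is -ln(0.8)/181 = 0.00123 per day, or about 3.7 first events per 100 participant-months of 30 days. Under the constant-hazard assumption this is the same whether the CP lasts 181, 195 or 211 days.

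**The case against.** The strongest case on the other side is that the effect is small, its direction is not fixed, and nothing formal rests on it.

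- **Size.** For a single preferred term with 5% background risk, the excess over 211 days is 0.8 points, or 0.3-0.6 at arm level with 40-80% touch-up. In 144-162 VOLUX participants that is about half to one person. With 48-54 controls, one control is about 2 points, and at 30% risk the 95% half-width of an arm difference is about 14-15 points. This stands: the artefact lies inside sampling noise. It is still a known systematic difference that can be removed cheaply.
- **Direction.** A reader might infer that VOLUX percentages are always inflated. The documents do not support that, because the extension of control CPs to optional treatment works the other way and can cancel or reverse the difference.
- **Consequence.** A reader might infer that the between-group AE difference cannot be read as a device effect at all. That does not follow from a shift of this size. The CP tables are descriptive, with no between-arm AE test, so type I error is not at issue. Treatment-related TEAEs, as judged by the treating investigator, arise mainly from the injections and depend little on background time. Section 5.6.3 also lists all TEAEs, so later windowing is possible.
- **Randomized comparison.** The Safety population is analysed as treated (SAP Table 4-1). The comparison is therefore randomized only to the extent that participants were treated as assigned.
- **A Day 181 cap as the main remedy.** Controls who decline treatment complete the study at Month 6, which may fall about 10 days early, near Day 171. The cap also leaves only 181 - 30 = 151 days after a touch-up, while Protocol 11.1.1 warns of side effects many months after treatment. This stands, so the cap belongs in a supporting display.

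**Conclusion.** The point holds in limited form. Table 5-1 gives CP lengths of 181 days (VOLUX without touch-up), about 211 days (with touch-up) and 181 to 195 days (control), and nothing in the AE analysis corrects for this. Crude all-cause TEAE percentages are therefore partly confounded with follow-up time.

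The range from about -0.4 to about +4 points rests on the assumed touch-up share and background risk, a constant hazard equal in both arms, and the two extremes of control CP length. The documents fix none of these, so neither the size nor the sign can be settled in advance. This is a matter of clear reporting. It does not invalidate the safety analysis, and it leaves the effectiveness analysis and its Month 6 anchor untouched.

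**What to change.** In SAP 5.6.3 and Table 5-9, for the between-group CP tables of all-cause TEAEs:

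1. Report participant-time in CP by arm.
2. Add exposure-adjusted rates per 100 participant-months: all events over total CP time, and participants with a first event over time to first event or end of CP.
3. As a supporting display, count TEAEs from initial treatment (VOLUX) or randomization (control) through a common Day 181, or to exit or optional treatment if earlier.
4. Keep the full-CP tables as planned, so that later events still appear beside the control arm.

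The cost is some SAP text, a few table columns and one derived date. The rates assume a roughly constant hazard, which events clustered after an injection do not follow, so they are best read for background all-cause events. The Day 181 display shortens follow-up after a touch-up and leaves a small inequality where a control's Month 6 visit comes early; a footnote should say so.

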5.6.4. Injection Site Responses

ISRs recorded in participant diaries after initial and touch-up treatments will be summarized for the VT population, and ISRs recorded after maintenance treatment will be summarized for the VMT population. The diary date and time will be compared with the treatment injection date and time to determine the corresponding treatment (ie, initial, touch-up, or maintenance) for each diary for the purposes of analysis. If there are multiple diary entries for any day, then the worse severity and maximum duration will be included in the summary for the corresponding symptoms analyzed. Descriptive statistics will be provided for the endpoints listed in [Table 5-10](#) for the initial treatment, touch-up treatment and maintenance treatment periods by predefined symptoms.

Table 5-10 **Injection Site Responses Analyses**

Endpoint	Description	Timing	Methodology
ISR severity	Maximum reported severity.	Initial, Touch-up, Maintenance	Categorical descriptive statistics
ISR duration	Duration from first instance of the symptom to the last instance of the symptom within the treatment period, where last instance means no further symptoms until the end of the 30-day diary period. Duration is derived as date of last ISR minus date of first ISR plus one, on the participant level, regardless of the side of the jaw.	Initial, Touch-up, Maintenance	Categorical descriptive statistics

Other symptoms of ISR entered in the e-diary by participants will be coded into medical terminologies by the medical safety physician. Other ISRs with “No,” “None,” or texts with a similar meaning will be coded as “N/A.” If other ISRs are coded as one of the prespecified symptoms (ie, redness, pain after injection, tenderness to touch, firmness, lumps/bumps, bruising, itching, and discoloration), then the participant will be counted only once based on the maximum severity and duration across the prespecified symptom entries and the coded terms. Other symptoms of ISR that are coded into terms beyond the list of prespecified symptoms will be summarized under “Other” symptoms in the summary tables for ISR. If a participant reported more than one non-prespecified terms of “Other ISR,” the participant will be counted once in the summary of “Other” symptoms for that treatment. The free texts entered by the participant, and the coded terms for “Other” symptoms will be included in the data listing.

If the incidence of any particular category of “Other” ISR is greater than 5%, then the severity and duration analyses described in [Table 5-10](#) will be performed for that specific category of the “Other” ISR.

ISR day will be derived as ISR date – most recent treatment date + 1.

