#### Study design:

This is a multicenter, evaluator-blinded, randomized, parallel-group, controlled study of the safety and effectiveness of VOLUX XC hyaluronic acid (HA) injectable gel to restore a loss of jawline definition. Successfully screened subjects will be randomized to either a treatment or control group (3:1 ratio, respectively).

Subjects randomized to the treatment group will receive treatment on Day 1. After treatment completion (initial and touch-up if touch-up administered), they will be followed for safety and effectiveness for 12 months, with an optional maintenance treatment at Month 12 and additional 3 months of follow-up for safety and effectiveness.

Subjects randomized to the control group will complete a 6-month no-treatment control period. After control period completion, they will have the option to exit the study or receive a delayed-treatment. After treatment completion (initial and touch-up if touch-up administered), subjects will be followed for effectiveness for 6 months and for safety for 12 months without optional maintenance treatment. After follow-up completion (12 months), they will exit the study.

At the Screening visit, after written informed consent (IC) has been given, the Treating Investigator (TI, or a designee) will document the subject's demographics, height, weight, vital signs, Fitzpatrick skin phototype, race, and history of sun exposure, smoking and tobacco use, and medical, surgical, dental, and cosmetic procedures. Female subjects of childbearing potential will undergo urine pregnancy testing. Subjects will undergo 3-dimensional (3D) facial digital images. The Evaluating Investigator (EI) will rate the subject on the 5-grade photonumeric Allergan Loss of Jawline Definition Scale (ALJDS) to determine eligibility for the study. The TI will ensure the subject's anatomy is amenable to at least 1-grade improvement on the ALJDS.

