# **6.2.3.2** Treatment Group: Follow-up/Maintenance Treatment Period

Follow-up visits for safety and effectiveness will occur at 1, 3, 6, 9, and 12 months after initial treatment (or touch-up, if applicable).

After completion of the Month 12 visit, subjects will be offered an optional maintenance treatment. Subjects who decline maintenance treatment will exit the study. Subjects who agree to receive maintenance treatment will be followed for 3 additional months and then exit the study.

The procedures and assessments to be performed at maintenance treatment and at the 4 follow-up visits (Day 3, Day 14, and Months 1 and 3) after maintenance treatment are identical to those after the initial treatment, with the exception that no touch-up will be offered and the product characteristics won't be recorded.

Subjects who are randomized to the treatment group and decide to exit the study at any point before the Month 12 visit must complete the Early Exit Visit procedures in addition to all applicable visit procedures.

The procedures and evaluations to be performed during the follow-up and maintenance treatment periods are listed by visit in Table 3.

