VOLUX Treated	
 ! Participants randomized and received VOLUX treatment at the beginning of the Control Period^b, or ! Participants randomized and received optional VOLUX treatment after the Control Period 	As treated
VOLUX Maintenance Treatment	Participants in the VT population who received VOLUX maintenance treatment	As treated

^a If a randomized control participant does not receive the optional treatment, the actual received treatment will be assigned as control treatment.

^b Control Period is defined in Section 5.1.

5. Statistical Analyses

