5.3.4. Supplementary Analyses

Descriptive statistics for the primary endpoint will be summarized for the mITT population during the control period (ie, Month 1, 3, and 6 after study treatment for the treatment group and after randomization for the control group). Additionally, descriptive statistics for the primary endpoint will be summarized for the VT and VMT populations, which includes all visits after study treatment (ie, Month 1, 3, 6, 9 and 12 for the VT population and Month 1 and 3 after maintenance treatment for the VMT).

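### The readable SAP summarizes initial injection site responses in everyone treated and maintenance responses only in acceptors, with no initial summary for those same acceptors

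*SAP*

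**What the plan says.** SAP 5.6.4 uses two populations. For the first treatment course, "ISRs recorded in participant diaries after initial and touch-up treatments will be summarized for the VT population". For the later one, "ISRs recorded after maintenance treatment will be summarized for the VMT population". Table 5-10 then gives maximum severity and duration for initial, touch-up and maintenance treatment, all descriptive.

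SAP Table 4-1 defines VMT as "Participants in the VT population who received VOLUX maintenance treatment". VT is wider and also takes in "Participants randomized and received optional VOLUX treatment after the Control Period". The protocol synopsis has those delayed-treatment controls "followed for effectiveness for 6 months and for safety for 12 months without optional maintenance treatment", so they can be in VT but never in VMT.

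Maintenance is optional and is offered after the Month 12 visit. Protocol 6.2.3.2 adds: "Subjects who decline maintenance treatment will exit the study". Protocol Table 3 records the reason for not receiving maintenance, but the readable SAP text plans no analysis of it.

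For adverse events, SAP 5.6.3 does more. For maintenance recipients, "their AEs reported during the three months in the initial treatment period will be summarized and presented in parallel" with the events of their maintenance period. Neither SAP 5.6.4 nor protocol 8.3.4 states an equivalent for ISRs. Procedural pain (SAP 5.6.5) is summarized for the treated and maintenance periods, which SAP 5.1 ties to VT and VMT respectively, again with no matched summary stated.

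**The concern.** Maintenance ISRs can be observed only in people who received maintenance, so using VMT for them is not a fault. The gap is on the other side: the initial-treatment ISRs of those same people are not shown separately.

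To be in VMT a participant must have been randomized to treatment, stayed to Month 12 and agreed to more injections. If any of this is related to how the first treatment was tolerated, the two sets of tables differ in membership as well as in treatment. A reader who sets them side by side could not tell whether a milder, or worse, maintenance profile describes repeat treatment or the people who chose it. What is at stake is the interpretation of a descriptive safety display. No endpoint, test or decision rule is affected.

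**Working it through.** **1. Expected size of VT, from the plan's own inputs.** SAP section 3 gives minimum randomized numbers of 144 (treatment) and 48 (control). It assumes 5% drop-out before initial treatment in the treatment group and 15% before optional treatment in the control group.

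- Treatment group treated: 144 × 0.95 = 136.8
- Delayed controls treated: 48 × 0.85 = 40.8
- Total: 177.6, or 136 + 40 = 176 with each arm rounded down. This reproduces the plan's figure of at least 176.
- Delayed controls as a share of VT: 40.8 / 177.6 = 23%

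**2. Expected size of VMT.** The documents give no uptake figure, so one is assumed. Let u be the share of treated treatment-group participants who go on to receive maintenance. The central value is 75%, with a range of 50% to 90%. The only guide is protocol 2.2, where the denominators in V25L-001 are 119 after initial or touch-up and 89 after repeat treatment (89/119 = 75%). The documents do not say that all 119 were offered repeat treatment, so this is not an acceptance rate.

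| u | VMT = 136.8 × u | VMT as share of all VT (177.6) |
|---|---|---|
| 50% | 68 | 39% |
| 75% | 103 | 58% |
| 90% | 123 | 69% |

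If delayed controls are tabulated in their own column, the comparable initial-treatment column is the 136.8, and VMT is simply u of it. Some mismatch therefore remains under either layout: 10% to 50% of that column is absent from VMT, or 31% to 61% of a pooled column.

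**3. Illustration of what selection alone could do (assumed inputs, no true change).** Let p be the proportion of treatment-group participants with a given ISR after initial treatment. Let r be the acceptance of maintenance among those who had it, relative to those who did not. Suppose each person's ISR status is the same at both treatments. Then

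rate among acceptors = p·r / [(1 − p) + p·r].

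Overall uptake cancels out of this formula, though it limits which values of r are possible. With p = 30%:

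| r | Calculation | Acceptors' rate | Apparent change (points) |
|---|---|---|---|
| 1.25 | 0.375 / 1.075 | 34.9% | +4.9 |
| 1.0 | 0.30 / 1.00 | 30.0% | 0 |
| 0.8 | 0.24 / 0.94 | 25.5% | −4.5 |
| 0.6 | 0.18 / 0.88 | 20.5% | −9.5 |
| 0.4 | 0.12 / 0.82 | 14.6% | −15.4 |

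At u = 75% every row is feasible. At u = 90%, r = 1.25, 0.6 and 0.4 are not, because they would need acceptance above 100% in one group. If ISR status varies from one treatment to the next, the shifts are smaller. Neither p nor r is in the documents. The table shows only that the artefact can be zero, or can go either way by several points.

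**4. Does the adverse event display already cover this?** Only in part. Under protocol 7.2 the treating investigator decides whether a diary ISR qualifies as an adverse event. Those that do reach the parallel display of SAP 5.6.3; the rest stay in the diary tables and have no matched summary.

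**The case against.** The strongest reply is that the plan makes no comparison. Protocol 8.3.4 has ISRs summarized separately for each treatment, and SAP 5.6.4 is descriptive throughout. Each table describes its own treatment in a properly labelled population. That stands. A reader might infer that the plan judges the safety of repeat treatment by setting these tables against each other, or that maintenance will look better tolerated than it is. The documents support neither inference. Protocol 2.2 reports that most ISRs in V25L-001 resolved within a week, while the maintenance decision comes about a year later, so a strong link between the two is not a given.

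Other points also carry weight:

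- SAP 5.6.3 gives no reason for its parallel display. Limiting the initial period to three months may be meant to equalize observation time, a need that ISR diaries of up to 30 days do not have. The display is thus a precedent for the format, not proof that ISRs were overlooked. It does still use the same participants in both columns.
- SAP Table 5-1 labels delayed controls separately from the VOLUX group, and SAP 5.1 groups VT as treated. One cannot assert that they are pooled in the initial ISR column.
- Table specifications are in a separate document (SAP section 1), which might include the display. The SAP itself should still state it.
- It is tempting to extend the point to ALJDS response, since SAP 5.3.4 says "descriptive statistics for the primary endpoint will be summarized for the VT and VMT populations". But SAP 5.5 and Table 5-6 are blanked out in the public copy, and item 15 of SAP 6.2.2 shows that Table 5-6 holds responder analyses of ALJDS. Whether a matched display exists there cannot be judged.

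None of this supplies the missing ISR summary in the readable SAP.

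**Conclusion.** The point holds as a minor, inexpensive improvement. The initial and maintenance ISR tables describe different sets of people, and the readable SAP plans nothing that shows the maintenance recipients' own initial ISRs beside their later ones. A descriptive difference between the tables could therefore come from who accepted maintenance.

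The size of any distortion cannot be estimated from the documents. It is zero if uptake is unrelated to ISRs. The shifts in the working, from a rise of 4.9 to a fall of 15.4 points at a 30% initial rate, are illustrations on assumed acceptance ratios and not predictions. The conclusion does not rest on them, nor on delayed controls being pooled. It rests on the two population definitions and on the absence of a matched summary in SAP 5.6.4 and protocol 8.3.4. Procedural pain in SAP 5.6.5 has the same structure.

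**What to change.** In SAP 5.6.4 and Table 5-10, keep the VT tables and add, for the VMT population, maximum ISR severity and duration after initial and after touch-up treatment, shown in parallel with that population's maintenance ISRs. Add the same for procedural pain in SAP 5.6.5.

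State the limit of the display in the SAP text. Injected volume is set by the treating investigator and may differ between treatments, and protocol 4.3.4 offers no touch-up after maintenance. The matched columns therefore remove the difference in who is counted, but do not isolate the effect of repeat treatment.

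The cost is some SAP wording and a few more table columns from data already being collected. Sample size, significance level and study conduct are unchanged.
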